Stereotactic Body Radiotherapy for Osseous Low Alpha-Beta Resistant Metastases for Pain Relief - SOLAR-P

Resident Investigator: [name]

Principal Investigator: [name]

Background

The use of stereotactic body radiotherapy (SBRT) has been a topic of interest in palliative approaches for managing metastatic disease. Advances in radiation planning and delivery allows clinicians to target lesions with higher, ablative doses to tumors, while minimizing dose to organs and tissues at risk. SBRT has been demonstrated to be effective in controlling local metastatic lesions, while delaying distant progression of disease within the context of several retrospective, and small prospective randomized trials (1,2).

The use of SBRT is appealing, in particular, for tumors with low alpha-beta ratios such as prostate cancer, breast cancer, renal cell carcinoma (RCC), melanoma, and sarcoma. Such tumors have inherent radioresistance to standard fractionation regimens, and benefit from dose escalation in order to yield more potent biological efficacy. Theoretically, this may lead to amplification of vascular damage, increased endothelial cell apoptosis, and enhanced antitumor immunity (3). Low alpha-beta tumors classically respond to higher doses per fraction, as demonstrated in pre-clinical studies for instance using renal cell cancer cell lines (4), and in clinical studies suggesting equivalent or improved local control using more hypofractionated radiation regimens (5,6). The higher doses in fewer fractions theoretically may overcome innate tumor radioresistance resulting in improved local control and symptom resolution.

Palliative radiotherapy (RT) has been common practice in managing painful bone metastases, and classically this has been administered in conventional fractionation schedules such as 20 Gray (Gy) in 5 fractions or 8 Gy in a single fraction. RT has been established an effective, low-risk approach for uncomplicated symptomatic bone metastases, and a meta-analysis showed overall response rate of 60% and complete response rate of 23-24% (7). Following RT, median time to onset of pain relief was 1-4 weeks, and median duration of response was 3-6 months. Multiple studies have shown no significant differences in outcomes between single fraction and multiple fraction regimens, though following single fraction there was a higher chance of retreatment (8-11).

Retreatment with palliative RT has also been shown to be effective following no response or symptomatic relapse after initial treatment. In the per-protocol analysis, the SC20 trial reported that patients retreated with 8 Gy/1 fraction and 20 Gy/5 fractions had pain response rates of 45% and 51%, respectively at 2 months post-treatment (12). Overall, 48% of patients who received their assigned treatment had reduced pain at the site of repeat radiation, regardless of whether or not they responded to their initial treatment. In addition, 68% had improved quality of life pain scores.

SBRT has shown promising early results in the management of bone metastases. In addition to its utility in spinal lesions, SBRT has been reported to improve local control in prostate cancer bone metastases with reductions of in-field failure in comparison to hypofractionated schedules (13), but it was unclear whether this translated into long term pain relief. Also, there has been some research in the use of SBRT in RCC bone metastases, given its resistance to conventional fractionation. One study showed that SBRT improved symptom control rates at 10, 12 and 24 months in comparison to standard external beam RT, with a median time to control of 2 weeks (14), but documentation of pain control was variably captured, and largely extrapolated from clinical notes. Other retrospective data in RCC, melanoma and sarcoma suggested a high degree of pain relief in patients treated with SBRT for spine metastases, however pain scores were not prospectively captured (15), and the study was likely to be underpowered to determine a significant effect. In addition, a recent phase II randomized trial that included patients with bone metastases from all disease sites (majority lung), showed that single fraction SBRT had higher rates of pain response at 2 weeks and 3 months compared to conventional fractionation (16). However, the degree of pain response in the control group was less than expected, the majority of the patients on this study did not have low alpha-beta tumors, and the radiation dose schedule in the conventional arm was not typical of standard practice (30 Gy in 10 fractions as compared to 8 Gy/1 fraction or 20 Gy/ 5 fractions).

Currently, there is a paucity of prospective data studying the use of SBRT for bone metastases originating from low alpha-beta tumors, with systematic reporting of changes in pain scores and analgesia use over time. The vast majority data looking at SBRT in bone lesions focuses on local control and survival, rather than more tangible outcomes in a palliative population including symptomatic control, durability of response (and need for retreatment), and patient reported quality of life; a component that is understudied in this group despite its tremendous value. Furthermore, SBRT for bone metastases has yet to become common practice given the limited evidence for its efficacy and uncertainty in regards to toxicity.

We propose an investigation of the potential benefits of SBRT for symptomatic bone metastases in patients with prostate cancer, breast cancer, RCC, melanoma, and sarcoma. We look to conduct a prospective cohort study (SOLAR-P) that is adequately powered to analyse efficacy in alleviating pain from bone lesions and compare this to well-established rates in literature for conventionally fractionated palliative RT. We will also assess the tolerability of this modality, toxicity rates, and effect on quality of life. If our results show that SBRT has a significant benefit on this population, the goal would be to pursue a larger randomized trial to confirm the findings.

Methods

Patient Population:

Patients will be accrued from the Juravinski Cancer Centre. Eligibility will be determined based on the criteria listed below, and informed consent will be established.

- Inclusion
 - Diagnosis of prostate cancer, breast cancer, renal cell carcinoma, or melanoma
 - Radiographic evidence of bone metastases requiring treatment for pain
 - BPI score of ≥ 2
- Exclusion
 - Spinal lesions
 - Severe or progressive neurological deficit
 - Impending (Mirels' score ≥ 9) or existing pathological fracture
 - Bone metastasis in a previously irradiated site
 - Active concurrent systemic therapy
 - > 5 lesions requiring treatment
 - Lesions > 5 cm in largest diameter
 - Life expectancy < 3 months
 - Age < 18
 - KPS < 50
 - Unable to provide informed consent

Primary Outcome:

- **Overall Pain Response at 3 months:** Assessed using the Brief Pain Inventory (BPI; Appendix A) and converting daily analgesic use to oral morphine equivalent (OME)
 - *Complete response* defined as BPI pain score of 0 with no increase in OME.
 - *Partial response* defined as BPI pain score of >0 , and either a reduction of 2 or more with no increase in OME, or no increase in BPI with a reduction in OME or at least 25%.
 - *Treatment failure* defined as worsening pain on BPI by 2 or more, $>50\%$ increase in OME, re-irradiation for pain/progression, or development of pathologic fracture.

Secondary Outcomes:

- **Overall Pain Response at 1 month and 6 months post SBRT:** Assessed using the BPI and response as described above.
- **Toxicity:** Acute (3 months or less), and late (greater than 3 months) adverse effects from RT will be recorded according to the Common Terminology Criteria for Adverse Events (CTCAE) 5.0 (17).
- **Patient-reported QoL:** QoL assessed by European Organization of Research and Treatment of Cancer Quality of Life -Questionnaire-Core-15-Palliative (EORTC QLQ-C15-PAL) and EORTC QLQ-Bone Metastasis 22 (EORTC QLQ-BM22), measured at 1, 3, and 6 months post SBRT (18,19).
- **Rate of Re-irradiation and Salvage Surgery due to symptomatic progression:** Patients requiring re-irradiation will not undergo treatment for at least 4 weeks following the study radiation course. Patients requiring salvage surgery for disease progression, instability, or pathologic fractures will be reported.

- **Local Control of Treated Lesions:** To be assessed retrospectively using standard of care follow-up imaging. Radiographic control evaluated based on Response Evaluation Criteria in Solid Tumors (RECIST) 1.1 (20).

Intervention and Evaluation

Pre-Treatment Evaluation:

Patient eligibility will be determined during the initial assessment which includes a physical examination and review of radiographic evidence of metastases. Fracture risk will be assessed based on Mirels' Staging System taking into account the clinical evaluation and imaging available. For patients with high clinical suspicion of impending fracture, further evaluation may be taken with plain film radiographs as per standard of care.

An initial BPI will be completed prior to treatment during a clinic visit, or over the phone. Use of analgesic medications will be recorded.

Treatment Plan:

Enrolled patients will receive the study dose of 15 to 20 Gy in 1 fraction to all painful bony lesions with SBRT. Planning and delivery will be conducted using a volumetric modulated arc therapy (VMAT) approach on our Varian Truebeam platform. Patients will be CT simulated, with a vac-lock immobilization. Use of 4DCT will be dependent on the area being treated. The gross tumor volume (GTV) will be defined as the visible abnormality based on CT imaging. The planning target volume (PTV) will be an additional 5 mm in all directions. The SBRT prescription will ensure that at least 95% of the PTV will be covered with the prescribed dose, and that at least 99% of the PTV will be covered by 95% of the prescription dose. Dose to organs at risk will be based on institutional guidelines for single fraction SBRT. Daily image guidance will be performed using cone beam CT aligning to relevant bony anatomy +/- PTV if visible.

Evaluation During Study:

The primary outcome will be overall pain response, measured using the BPI. Patients will be assessed using the BPI at baseline, and then at 1 month, 3 months, and 6 months following the completion of the SBRT treatment course. Responses will be obtained by patient self-reported questionnaires in clinic or by telephone follow-up. The sum of responses will dictate the overall response to treatment. Patients will be seen once for treatment review during their SBRT course to document acute toxicity. They will also be assessed at the 1 month, 3 month, and 6 month intervals to record acute and late toxicity using CTCAE version 5.0. Quality of life will be measured using the EORTC QLQ-C15-PAL and BM22 questionnaires at the same timepoints.

Sample Size and Statistical Analysis

Sample size:

The estimated pain response at 3 months using cRT is approximately 60% (null hypothesis is that SBRT will have a response of 60% as well). However, we postulate that the pain response at 3 months using SBRT will be 80% (alternative hypothesis). Given 80% power, two-sided alpha of 0.05, we will require 41 patients to test this hypothesis using a one sample binomial test. We plan to recruit 45 patients to account for any losses to follow-up.

Statistical Analysis:

The observed proportion of pain response at 3 months with SBRT will be compared to the null value of 0.6 using a one sample binomial test. The corresponding 95% confidence interval (CI) around the observed proportion will be calculated using the Wilson score method.

[figure not shown]
Study Timeline

0-12 Months: Patient accrual, consent, RT planning and delivery.

12-18 Months: Ongoing follow-up of study patients, planned assessments at designated intervals for pain, toxicity and quality of life parameters.

18-24 Months: Data analysis, reporting and publication phase.

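### A probable one-word slip in the partial-response definition leaves the 25% OME threshold without effect as printed, in the rule that feeds the only hypothesis test

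*Protocol*

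**What the plan says.** The Primary Outcome section of the protocol (under Methods) defines response from the Brief Pain Inventory (BPI) and daily OME.

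- Complete response is "defined as BPI pain score of 0 with no increase in OME".
- Partial response requires a BPI score still above 0 and one of two routes. The pain route is "either a reduction of 2 or more with no increase in OME". The analgesic route is "no increase in BPI with a reduction in OME or at least 25" percent.

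The Secondary Outcomes section reuses the definition at 1 and 6 months: "Assessed using the BPI and response as described above". The Statistical Analysis section states the one hypothesis test: "The observed proportion of pain response at 3 months with SBRT will be compared to the null value of 0.6".

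The OME reduction threshold appears only in the partial-response sentence. The complete-response rule has no reduction threshold, the treatment-failure rule concerns OME increases, and the sections on evaluation and analysis do not restate the rule.

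**The concern.** As printed, the analgesic route is satisfied by a reduction in OME of any size, and the words about 25% form an alternative with no object. One patient's data can therefore be classified in two ways. Take BPI 7 at baseline and 7 at 3 months, with OME going from 60 to 55 mg/day. This patient is a partial responder on the literal text and a non-responder under a 25% minimum.

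The sentence is operative: it decides who counts as a responder in the primary analysis. The study has a single arm and a fixed comparison value, so no concurrent control group classified by the same rule would absorb a looser numerator. An unresolved reading also leaves room to settle the rule after outcomes have been seen.

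**Working it through.** **1. Logic of the sentence.** Let A be the patients with any OME reduction and B those with a reduction of at least 25%, all with BPI not increased and still above 0. Every member of B is in A, so A or B equals A, and the 25% removes nobody. With *of* in place of *or*, the qualifying set is B. The patients whose class depends on the word are those in A but not in B who do not already respond by the pain route. They have a BPI that is unchanged or has fallen by less than 2 points, with an OME fall of less than 25%. In the example above, (60 − 55)/60 = 8.3%, so that patient is in this group.

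**2. Direction.** Because B lies inside A, the literal reading can only add responders.

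**3. The plan's own sample size.** Inputs from the Sample size section: null 0.60, alternative 0.80, 80% power, two-sided alpha 0.05, 41 patients.

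- Normal approximation: n = [(1.960·√(0.6·0.4) + 0.842·√(0.8·0.2)) / 0.2]² = [(0.960 + 0.337)/0.2]² ≈ 42.0, within about one patient of the stated 41.
- Binomial check at n = 41 with a score cut-off: 31 responders give z = (31/41 − 0.6)/√(0.24/41) = 2.04, so the test rejects at 31 or more. Power is 81.8% and the upper-tail error 2.7%. This fits the stated 41.
- Exact test with an upper tail of at most 0.025: it rejects at 32 or more of 41.

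None of this depends on the disputed word.

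**4. What a literal application could do.** Assume the true rate under a 25% minimum is 0.60, and that a further share q of all patients counts only because of an OME fall below 25%. The protocol gives no value for q, so a range is shown. The chance of a significant superior result is P(X ≥ r), with X binomial(n, 0.60 + q).

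| Assumed q (percentage points) | Exact, n = 41, r = 32 | Score, n = 41, r = 31 | Exact, n = 45, r = 34 |
|---|---|---|---|
| 0 | 1.2% | 2.7% | 2.2% |
| 2.5 | 2.6% | 5.5% | 4.6% |
| 5 | 5.2% | 10.2% | 9.0% |
| 10 | 17.0% | 27.5% | 26.2% |

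Each reclassified patient moves the observed rate by 1/41 = 2.4 points.

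**The case against.** The strongest reply is that this is a one-letter slip. The phrase about 25% has no object as an alternative, and the only reading that gives the number a purpose is a minimum of 25%. A reader might infer from the literal text that the investigators chose to count any OME reduction. The protocol does not support that: it states a threshold, and the proposed correction only restores it. The text at hand was also read from PDF by a program, so the source page should be checked. This reply stands, and it makes the point a drafting error and not a design choice. It does not remove the need for correction, because assessors and programmers work from the text and no other sentence settles it.

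A reader might also infer that the primary response rate will be biased upwards because small OME falls are common with as-needed dosing. The protocol gives no data on baseline opioid use, dosing pattern or OME variability. Patients taking no opioid at baseline cannot qualify by this route, and those whose BPI falls by 2 or more without an OME increase already respond by the other. Only a residual group of unknown size is affected, and only if the slip is applied as written. At an excess of up to 2.5 points the exact test at n = 41 stays close to the nominal 2.5% upper tail.

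Nor is there a case for divergent readings between sites, since accrual is at one cancer centre.

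**Conclusion.** The point holds as a drafting error in the primary endpoint definition. Read literally, the sentence gives the 25% no effect, and the rest of the protocol does not resolve it. The error sits in the rule behind the 3-month comparison with 0.6 and behind the 1- and 6-month outcomes, and it can act only in favour of SBRT.

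Its size is unknown. If a 25% minimum is applied in practice, the effect is zero. The probabilities tabulated above are conditional on three assumptions: a true rate of 60% under the 25% minimum, literal application of the printed words, and an assumed excess share. They illustrate sensitivity and are not an estimate of the trial's type I error.

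**What to change.** Check the source page. If it carries the same word, correct the analgesic route to require that BPI has not increased and that daily OME has fallen by at least 25% from baseline. That is the protocol's own figure with the slip removed. Make the correction before any 3-month outcome is classified, so that the reading cannot depend on the results.

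No separate instruction for 1 and 6 months is needed, because the Secondary Outcomes section already refers back to this definition. Nor is an added statement that smaller reductions are non-response, since that follows once the threshold is restored.

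The cost is one corrected sentence. The sample size stays at 41 evaluable and 45 recruited. The observed response rate may be slightly lower than under the literal wording.

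### No quality-of-life questionnaire is expressly scheduled before SBRT, so the text as written yields no within-patient QoL change across treatment

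*Protocol*

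**What the plan says.** Four parts of the protocol bear on when quality of life is measured.

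- **Methods, Secondary Outcomes.** The two EORTC questionnaires are "measured at 1, 3, and 6 months post SBRT (18,19"). No baseline is listed.
- **Intervention and Evaluation, Pre-Treatment Evaluation.** For patient-reported and symptom data this section gives two items: "An initial BPI will be completed prior to treatment during a clinic visit, or over the phone" and "Use of analgesic medications will be recorded". It also covers examination, imaging review and fracture risk. Neither EORTC form appears.
- **Evaluation During Study.** The pain schedule comes first: "Patients will be assessed using the BPI at baseline, and then at 1 month, 3 months, and 6 months following the completion". Toxicity follows: "Patients will be seen once for treatment review during their SBRT course to document acute toxicity", and then "They will also be assessed at the 1 month, 3 month, and 6 month intervals to record acute and late toxicity". The next sentence reads: "Quality of life will be measured using the EORTC QLQ-C15-PAL and BM22 questionnaires at the same timepoints".
- **Study Timeline.** The text mentions assessment of pain, toxicity and quality of life at intervals that it does not list. A figure beside it is not readable in the copy reviewed.

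The Background says the study will assess the effect of SBRT on quality of life, and it describes patient-reported quality of life as understudied in this population.

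**The concern.** The study is a single cohort with no concurrent control, and the only external comparison it specifies is for pain response. For quality of life, the patient's own score before treatment is therefore the only reference that the protocol could provide. Without it, the QoL data describe levels after treatment and drift after the first month. They cannot show whether patients improved or worsened after SBRT.

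Timing adds to the problem. The Background puts the median onset of pain relief after palliative RT at 1 to 4 weeks. If SBRT acts on a similar scale, and quality of life follows pain (both are assumptions), much of any change could be over before the first scheduled form at 1 month.

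This cannot be left to a statistical analysis plan. Such a plan can define change from baseline, but it cannot supply a questionnaire that was never given. The loss is permanent for each patient treated without one.

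**Working it through.** The protocol states no figure on this point, so there is nothing to reproduce. The check sets the passages side by side and counts the comparisons that each reading permits.

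**Step 1: express mentions of a form completed before SBRT**

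| Instrument | Secondary Outcomes | Pre-Treatment Evaluation | Evaluation During Study | Count |
|---|---|---|---|---|
| BPI | no | yes | yes | 2 |
| QLQ-C15-PAL and QLQ-BM22 | no | no | not expressly | 0 |

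**Step 2: what the QoL sentence in Evaluation During Study could refer to**

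- *Reading A, the toxicity follow-up visits.* These are in the sentence immediately before. They give 1, 3 and 6 months, which matches the Secondary Outcomes list exactly.
- *Reading B, the BPI schedule.* This stands earlier in the same paragraph. It gives baseline and 1, 3 and 6 months, so it adds a baseline to the Secondary Outcomes list without contradicting the three follow-up times.
- *Reading C, all toxicity assessments, including the review during the SBRT course.* This gives four times, but the first falls during treatment and does not appear in the Secondary Outcomes list.

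**Step 3: within-patient contrasts per scale**

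With k timepoints the number of pairwise contrasts is C(k,2) = k(k − 1)/2.

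| Reading | k | C(k,2) | Contrasts that start from a pre-SBRT score |
|---|---|---|---|
| A | 3 | 3 × 2 / 2 = 3 (3 vs 1, 6 vs 1, 6 vs 3 months) | 0 |
| B | 4 | 4 × 3 / 2 = 6 | 3 (1, 3 and 6 months vs baseline) |
| C | 4 | 4 × 3 / 2 = 6 | 0 (the earliest score is taken during the course) |

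Only Reading B gives a change from before treatment, and it requires passing over the nearest antecedent.

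**Step 4: what the stated aim needs**

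An effect on quality of life in an uncontrolled cohort needs at least one contrast that spans treatment. The Background reports quality of life in the cited retreatment trial in the same way: 68% had improved QoL pain scores. That sets no analysis for this study, but it shows the kind of result that readers would expect, and it requires a pre-treatment score.

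**The case against.** The strongest reply is that this is an ambiguity and not an omission. Evaluation During Study is the operational schedule, and the only complete questionnaire schedule in that paragraph is the BPI's, which has a baseline. Because the EORTC instruments are also patient questionnaires, Reading B is natural. The Secondary Outcomes list is weak evidence against it, because this protocol habitually names outcomes by follow-up time: the primary outcome is headed "Overall Pain Response at 3 months" although a baseline BPI is plainly scheduled. The unreadable figure might also contain a schedule.

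Much of this stands. The text does not prove that a baseline was meant to be excluded, and the contents of the figure are unknown. But the parallel with pain fails at the decisive place: the pain baseline is spelled out twice elsewhere, and the QoL baseline is not spelled out at all. Reading B also leaves the Pre-Treatment Evaluation, where a coordinator would look for what to collect before treatment, without either EORTC form. Two coordinators could follow this text in good faith and collect different data. Even if the figure shows a baseline, the wording would still need to be aligned with it.

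It is also fair to say that the contrast counts measure neither bias nor precision. They show only which comparisons would exist. Quality of life is one of several secondary outcomes, and even with a baseline the design supports only a before-and-after description.

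**Conclusion.** The concern holds, within limits. No readable part of the protocol expressly schedules either EORTC questionnaire before SBRT. Followed as written, the Secondary Outcomes and Pre-Treatment sections leave 0 of 3 within-patient contrasts spanning treatment, against 3 of 6 if a baseline were collected.

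This rests on two conditions: that staff take the QoL sentence to refer to the toxicity follow-up visits, or work from the outcome list alone; and that the unreadable figure does not settle the matter. Confidence is moderate for that reason. If the BPI schedule was meant, the defect is only one of wording.

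The primary endpoint has an explicit baseline and is not affected. The point should be fixed because the possible loss is the only before-and-after view of a named secondary outcome, and it cannot be repaired after treatment.

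**What to change.** State the baseline in three places so that they agree:

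1. **Secondary Outcomes, Patient-reported QoL:** list a baseline assessment before SBRT ahead of the 1, 3 and 6 month assessments.
2. **Pre-Treatment Evaluation:** name the QLQ-C15-PAL and the QLQ-BM22 beside the initial BPI.
3. **Evaluation During Study:** replace the reference to unspecified shared timepoints with the explicit list: baseline before SBRT, then 1, 3 and 6 months after it.

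Check the figure beside the Study Timeline against this list.

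The cost is two short questionnaires per patient at the pre-treatment contact where the BPI is already completed, and three short wording changes. Sample size, the primary analysis, eligibility and treatment do not change. Reports should still describe the QoL result as a before-and-after change in a single arm.

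### No CTCAE grade is planned before SBRT, so non-pain symptoms must be attributed to radiotherapy without a recorded baseline

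*Protocol*

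**What the plan says.** The Secondary Outcomes make toxicity a named endpoint and word it causally: "adverse effects from RT will be recorded according to the Common Terminology Criteria for Adverse Events (CTCAE) 5.0". Acute means up to 3 months and late means after that.

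The timing is in Evaluation During Study. The first toxicity record is made on treatment: "Patients will be seen once for treatment review during their SBRT course to document acute toxicity". The next sentence gives the remaining times: "They will also be assessed at the 1 month, 3 month, and 6 month intervals to record acute and late toxicity using CTCAE version 5.0".

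The Pre-Treatment Evaluation begins with eligibility: "Patient eligibility will be determined during the initial assessment which includes a physical examination and review of radiographic evidence of metastases". It adds a Mirels' assessment of fracture risk and then two items of symptom data: "An initial BPI will be completed prior to treatment during a clinic visit, or over the phone", and "Use of analgesic medications will be recorded". No CTCAE grading or general symptom inventory is listed.

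Pain is handled differently: "Patients will be assessed using the BPI at baseline, and then at 1 month, 3 months, and 6 months". Quality of life, under Secondary Outcomes, is "measured at 1, 3, and 6 months post SBRT", with no pre-treatment time named there.

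**The concern.** The patients have metastatic cancer with painful bone lesions, and a KPS as low as 50 is allowed. It is foreseeable that some will have gradeable symptoms before any radiation, although the documents do not say how many. A grade 2 fatigue at 1 month could then be new, worse, unchanged or improved, and the record would not show which.

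A randomised comparison would supply a background rate for such symptoms. This cohort has no comparator, so the pre-treatment grade is the only internal reference available. The Background gives uncertainty about toxicity as one reason SBRT is not yet common practice, and it promises toxicity rates from this study. Those rates could be too high if symptoms already present are counted, or too low if real worsening is put down to the disease. Grades not collected before treatment cannot be recreated by any later analysis plan.

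**Working it through.** The Protocol states no expected toxicity rate, threshold or toxicity-based sample size, so there is no figure of its own to reproduce. Its design figures (60% against 80% response, 41 patients, 45 recruited) belong to the pain test and do not depend on this point. The check is a reading of the schedule, followed by an illustration.

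**Schedule as stated in the visible text**

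| Measure | Before SBRT | During course | 1, 3, 6 months |
|---|---|---|---|
| BPI | yes | not stated | yes |
| Analgesic use | yes | not stated | needed for the response definition |
| Physical examination | yes, for eligibility | not stated | not stated |
| QoL questionnaires | not stated | not stated | yes |
| Toxicity | not stated | one review | yes, CTCAE 5.0 |

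Two entries might be thought to fill the gap:

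- **The on-treatment review.** Treatment is a single fraction. The review is not said to come before the dose, and its stated purpose is to document acute toxicity, so it is not a baseline.
- **The questionnaires.** Evaluation During Study places them at the same times as the assessments just described, and the sentence immediately before concerns toxicity at 1, 3 and 6 months. If a baseline were read into it, patient-reported scores would help but would still not be CTCAE grades.

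**Illustration on assumed rates (none are in the documents)**

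For one CTCAE term, let t be the proportion of patients in whom radiotherapy makes the term appear or worsen. Let b be the proportion who already have it before SBRT. Assume that t and b are independent and that existing symptoms persist to follow-up.

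Upper bound, with every symptom present counted as toxicity: recorded rate = 1 − (1 − t)(1 − b).

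| b | t = 5% | t = 10% |
|---|---|---|
| 10% | 1 − 0.95 × 0.90 = 14.5% | 1 − 0.90 × 0.90 = 19% |
| 20% | 1 − 0.95 × 0.80 = 24% | 1 − 0.90 × 0.80 = 28% |
| 30% | 1 − 0.95 × 0.70 = 33.5% | 1 − 0.90 × 0.70 = 37% |

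In 45 patients with t = 10%, this means 45 × 0.10 = 4.5 expected true cases recorded as 45 × 0.19 = 8.6 up to 45 × 0.37 = 16.7.

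The opposite error arises if worsening in patients who already had the symptom is always put down to disease. The recorded rate is then t(1 − b). With t = 10% this is 0.10 × 0.90 = 9% at b = 10%, and 0.10 × 0.70 = 7% at b = 30%.

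**The case against.** A reader might infer that pre-existing symptoms cannot be separated from toxicity at all. The documents do not support that. The endpoint is limited to effects caused by radiotherapy, so the recorder must attribute each event and not simply count what is present. Pain has a baseline BPI score. Analgesic use is recorded, which gives a likely cause of constipation though not its grade. The eligibility examination may also leave notes on other findings.

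The exclusions narrow the problem further. Existing or impending fracture, serious or advancing neurological deficit, earlier radiation to the site and ongoing systemic treatment all bar entry, so several sources of pre-existing events are removed.

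Nor is CTCAE toxicity the trial's only safety result, as might also be inferred. Pathologic fracture, re-irradiation and salvage surgery are reported separately and need no CTCAE baseline.

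Toxicity is also a secondary outcome, with no test, threshold or stopping rule in the Protocol attached to it. How an event is defined for analysis may properly sit in a statistical analysis plan that is not shown.

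All of this stands, and it limits the point. It does not supply a baseline grade for fatigue, nausea, constipation and similar terms. Requiring attribution makes the earlier grade more useful, because without it the judgement has no systematic record to rest on. An analysis plan can define worsening, but cannot supply the grade from which worsening is measured.

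**Conclusion.** The point holds in a limited form. In the visible text, CTCAE toxicity recording starts on treatment and no pre-SBRT grade is stated. Non-pain symptoms must then be attributed to radiotherapy without a recorded starting grade, in a single-arm study of symptomatic patients. The reported toxicity rate may be biased in either direction, and the documents do not allow the size to be estimated.

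The range of 19% to 37% for a true 10% is a hypothetical upper bound. It assumes 10% to 30% already symptomatic, independence, full persistence and no attribution at all. It should not be read as a forecast, because the endpoint's own wording requires attribution.

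One reservation: a figure beside the Study Timeline could not be read. If it is an assessment schedule that includes a pre-treatment CTCAE grade, the point falls. The primary pain response has its own baseline and is unaffected. This is a worthwhile, inexpensive improvement to a secondary outcome and does not threaten the trial's main conclusion.

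**What to change.** In the Pre-Treatment Evaluation, add CTCAE 5.0 grading of the relevant terms at the existing initial assessment, before SBRT. In the Toxicity outcome, or in the statistical analysis plan, state that a toxicity event is a new term or an increase over the pre-SBRT grade. An all-grade table can be shown alongside. The data collection has to be in the Protocol; the counting rule can be in either document.

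The cost is one extra form at a visit already planned and one sentence of definition, with no extra visit and no change to treatment or to the primary analysis. A baseline grade will not separate radiotherapy effects from new symptoms of disease progression after treatment, so attribution is still needed. It does remove the part of the ambiguity that comes from symptoms already present.
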